#### 2.2.4 **Analysis in Response to COVID-19 Impact**

As the Coronavirus Disease 2019 (COVID-19) pandemic has spread around the globe, the following analysis mechanism will be implemented to minimize the potential confounding effect from this emerging

## Statistical Analysis Plan

infectious disease for the trial primary and secondary endpoints set forth in assessing the trial success and labeling claims. In alignment with the guidance document “FDA Guidance on Conduct of Clinical Trials of Medical Products during COVID-19 Public Health Emergency” updated on 03-June-2020, additional consideration was given to the impact of the COVID-19 pandemic on the primary endpoint analyses for this study. As such, prespecified methods are included in the sections that follow to indicate the handling of any outcomes impacted by COVID-19 as well as efforts to minimize missing endpoint data during the COVID-19 pandemic. Specific analyses to address COVID-19 impacts are included in relevant subsections in Section 2.3.

### 2.3 Endpoint Analysis

#### 2.3.1 Primary Endpoints

##### 2.3.1.1 Primary Safety Endpoint (Portico NG cohort)

The primary safety endpoint for the Portico NG cohort is all-cause mortality at 30 days post index procedure.

The proportion of Portico NG subjects experiencing a primary safety endpoint will be estimated from the binomial model. COVID-19 relatedness of mortality will be adjudicated by the Clinical Events Committee (CEC), and any 30-day death that is adjudicated as COVID-19 related will be excluded from the primary analysis (i.e., from both numerator and denominator). The 95% confidence intervals will be calculated using the exact Clopper-Pearson method. The estimated primary safety endpoint rate at 30 days will be descriptively compared with the all-cause mortality rates (and 95% confidence intervals) of FDA approved TAVR devices studied in the same patient population (e.g., high and extreme risk), and additional published data on high and extreme surgical risk subjects available at the time of PMA submission, as described in the CIP.

The analysis population will include subjects who undergo a Navitor implant attempt that is described in Section 2.1.1, including subjects who withdraw or are lost to follow-up prior to 30-day visit.

##### 2.3.1.2 Primary Safety Endpoint (Titan cohort)

The primary safety endpoint for the Titan cohort is all-cause mortality at 30 days post index procedure.

The proportion of Titan subjects experiencing a primary safety endpoint will be estimated from the binomial model. COVID-19 relatedness of mortality will be adjudicated by the Clinical Events Committee (CEC), and any 30-day death that is adjudicated as COVID-19 related will be excluded from the primary analysis (i.e., from both numerator and denominator). The 95% confidence intervals will be calculated using the exact Clopper-Pearson method. The estimated primary safety endpoint rate at 30 days will be descriptively compared with the all-cause mortality rates (and 95% confidence intervals) of FDA approved large valve TAVR devices studied in the same patient population (e.g., high and extreme risk) as well as results from the Portico NG cohort.

The analysis population will include subjects who undergo a Navitor Titan implant attempt that is described in Section 2.1.1, including subjects who withdraw or are lost to follow-up prior to 30-day visit.

## Statistical Analysis Plan

### 2.3.1.3 Primary Effectiveness Endpoint (Portico NG cohort)

The primary effectiveness endpoint for the Portico NG cohort is moderate or greater paravalvular leak at 30 days.

Let  $\pi$  be the proportion of Portico NG subjects who experience a primary effectiveness endpoint event at 30 days. The following hypothesis will be tested:

$$H_0: \pi \geq 8.5\%$$

$$H_a: \pi < 8.5\%$$

$\pi$  will be estimated as a binomial proportion. The hypothesis will be tested at the 0.05 significance level and the null hypothesis will be rejected if the 95% upper confidence bound (UCB) for the proportion,  $\pi$ , is less than the performance goal of 8.5%. The results for the primary effectiveness endpoint will be considered successful if the null hypothesis is rejected. If a subject was unable to have an echocardiogram performed during the 30-day visit window (+21 days) due to the COVID-19 pandemic, sites were instructed to perform the echocardiographic imaging as soon as possible after this visit window and submit a protocol deviation. For the purpose of primary effectiveness endpoint analysis, all echocardiographic imaging submitted for the 30-day time point (including the out of window exams) will be used for analysis.

The analysis will include both the attempted population and the implanted population that are described in Section 2.1 and who have 30-day paravalvular leak status as determined by the echocardiography core laboratory, with the analysis on the implanted population as the primary analysis.

### 2.3.1.4 Primary Effectiveness Endpoint (Titan cohort)

The primary effectiveness endpoint for the Titan cohort is moderate or greater PVL at 30 days post index procedure.

The proportion of Titan subjects experiencing a primary effectiveness endpoint will be estimated from the binomial model. The 95% confidence intervals will be calculated using the exact Clopper-Pearson method. The estimated primary effectiveness endpoint rate at 30 days will be descriptively compared with 30-day moderate or greater PVL rates (and 95% confidence intervals) of FDA approved large valve TAVR devices studied in the same patient population (e.g., high and extreme risk) as well as results from the Portico NG cohort.

The analysis will include both the attempted population and the implanted population that are described in Section 2.1 and who have 30-day paravalvular leak status as determined by the echocardiography core laboratory.

### 2.3.2 Secondary Endpoint

The secondary endpoint is a non-hierarchical composite of all-cause mortality, disabling stroke, life threatening bleeding, acute kidney injury (stage 3), or major vascular complications at 30 days. This endpoint will be analyzed for both the Portico NG and Titan cohorts separately.

The proportion of subjects experiencing a secondary endpoint will be estimated from the binomial model. COVID-19 relatedness of secondary endpoint events will be adjudicated by the CEC, and any 30-day secondary endpoint event that is adjudicated as COVID-19 related will be excluded from the primary analysis (i.e., from both numerator and denominator). The 95% confidence intervals will be calculated

## Statistical Analysis Plan

using the exact Clopper-Pearson method. As described in the CIP, the estimated secondary endpoint rate at 30 days will be descriptively compared with rates observed with FDA approved TAVR devices studied in the same patient population (e.g., high and extreme risk), including the observed rates and 95% confidence intervals from published sources and data from FDA approved devices available at the time of PMA submission.

The analysis population will include subjects who undergo an implant attempt that is described in Section 2.1.1, including subjects who withdraw or are lost to follow-up prior to 30-day visit.

### 2.3.3 Descriptive Endpoints

Hemodynamic outcomes such as mean gradient, effective orifice area (EOA), paravalvular leak, etc. will be analyzed in the Implanted population described in Section 2.1.2, other descriptive endpoints will be analyzed in the Attempted population described in Section 2.1.1. All analyses will be performed on available data.

## 2.4 Sample Size Calculations

The total sample size required for the Portico NG cohort (to ensure adequate number of subjects for analysis of the primary endpoints) is [REDACTED] subjects.

Up to a total of [REDACTED] subjects will undergo a Navitor implant attempt to allow for analysis of the primary effectiveness endpoint.

For the Titan cohort, a total of [REDACTED] analysis provides an adequate sample size to descriptively compare to results from competitor studies of a larger valve size (e.g., Evolut R 34mm) and the Portico NG cohort.

## 2.5 Interim Analysis

No formal statistical rule for early termination of the trial is defined. Interim study reports may be produced for regulatory or reimbursement purposes.

## 2.6 Timing of Analysis

The analysis for the PMA submission will be conducted on a dataset locked after a minimum of [REDACTED] analysis subjects in the Portico NG cohort have had a 30-day study visit and have PVL data assessed by the echocardiography core laboratory. As stated in section 1.3, an analysis of the first [REDACTED] subjects (with a Navitor implant attempt) with 30-day follow-up data will be provided to support the CE Mark submission.

Data from the Titan cohort will be analyzed independently from the Portico NG cohort. The analysis for the Titan cohort will be conducted on a dataset locked after 60 analysis subjects have had a 30-day study visit and have PVL data assessed by the echocardiography core laboratory, excluding any subjects who die or are lost to follow-up within 30 days.

## 2.7 Study/Trial Success

Study success will be determined independently for the Portico NG and Titan cohorts. The Portico NG cohort will be considered successful if the rate for the primary safety endpoint (all-cause mortality within 30 days) is within expected ranges as compared to previous commercially approved devices studied in

## Statistical Analysis Plan

the same patient population (e.g., high and extreme surgical risk) and the null hypothesis is rejected for the primary effectiveness endpoint (moderate or greater PVL at 30 days).

The Titan cohort will be considered successful if [REDACTED] deaths occur within 30 days of the index procedure in [REDACTED] analysis subjects.

### 2.8 Subgroups for Analysis

Subgroup analyses may be performed to examine the consistency of the primary endpoints across baseline risk categories, valve sizes implanted, region (US vs OUS), and sex (male vs female). KM estimates on the primary endpoints event will be reported along with 95% confidence intervals.

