## Clinical Investigation Plan

To support PMA approval of the Navitor Valve, data from a minimum of 152 subjects who undergo a Navitor implant attempt (excluding roll-ins) will be analyzed and at least 40 of the 152 analysis subjects will be implanted with a 23 mm or 25 mm Navitor valve, with at least 10 subjects receiving a 23 mm valve. To ensure sufficient number of subjects for primary endpoint analysis (described in detail in section 8.3), a total of 169 subjects may undergo a Navitor implant attempt in the PMA cohort for the 23-29mm Navitor sizes (Portico NG cohort). Furthermore, at least 50% of the subjects in the Portico NG analysis cohort (n=85 subjects) will be enrolled at sites in the United States.

A separate cohort of 60 subjects (Titan cohort) will undergo an implant attempt with the Navitor Titan valve. Data from the Titan cohort will be analyzed separately to support submissions for regulatory approval. At least 50% of the subjects in the Titan analysis cohort (n=30 subjects) will be enrolled at sites in the United States. Prospective data from Titan subjects enrolled under a separate, regional OUS protocol may be combined with US subjects to meet the minimum required sample size for the PMA submission. Importantly, both protocols enroll high and extreme surgical risk subjects with severe symptomatic AS who undergo Navitor Titan valve implantation with the FlexNav Delivery System in a premarket setting and are aligned in terms of inclusion/exclusion criteria, devices being studied, training requirements and Instructions for Use, follow-up requirements and data collection. Furthermore, subjects enrolled in the Titan cohort will undergo the same screening, baseline, procedure and follow-up assessments as the Portico NG cohort.

In addition, up to a total of 20 roll-in subjects may be enrolled and undergo a Navitor implant attempt. While there is no pre-specified minimum number of extreme risk patients required for the study, a maximum of 20% of the analysis population may be classified as extreme risk (n=33 subjects for the Portico NG cohort and n=12 for the Titan cohort) to enroll a similar patient population as the Portico IDE and FlexNav studies. No investigational site may enroll more than 20% of the total analysis population (n=33 for the Portico NG cohort and n=12 for the Titan cohort).

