### 8.5 Subgroup Analysis

No subgroup analyses are planned for this clinical study.

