#### 2.2.2 **Descriptive Statistics for Categorical Variables**

For categorical variables (e.g. gender, diabetic status, etc.), results will be summarized with subject counts and percentages/rates, with exact 95% Clopper-Pearson confidence intervals, when specified.

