#### 2.2.3 **Survival Analyses**

Survival analysis will be conducted to analyze time-to-event variables. Subjects without events will be censored at the time of analysis. Survival curves will be constructed using Kaplan-Meier estimates and Greenwood standard errors.

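### If the optional subgroup analyses are run, the Kaplan-Meier method in SAP 2.8 gives no usable 95% interval for 30-day mortality in any subgroup without a death

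*SAP*

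**What the plan says.** SAP 2.8 makes the subgroup work optional: "Subgroup analyses may be performed to examine the consistency of the primary endpoints across baseline risk categories, valve sizes implanted", and it goes on to list region and sex. If the work is done, the method is fixed for both primary endpoints: "KM estimates on the primary endpoints event will be reported along with 95% confidence intervals".

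SAP 2.2.3 is the only place that says how Kaplan-Meier precision is obtained: "Survival curves will be constructed using Kaplan-Meier estimates and Greenwood standard errors". It names no transformation for the confidence interval and gives no rule for a group without events.

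For the same mortality endpoint in the full cohort, SAP 2.3.1.1 uses a binomial proportion: "The 95% confidence intervals will be calculated using the exact Clopper-Pearson method". SAP 2.3.1.2 does the same for Titan. SAP 2.2.2 offers the same exact method for categorical variables generally, "with exact 95% Clopper-Pearson confidence intervals, when specified".

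Protocol 8.5 reads: "No subgroup analyses are planned for this clinical study". The opening of Protocol section 8 nevertheless lists subgroup analysis among the details to be kept in the SAP.

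**The concern.** The subgroup display is meant to show whether the primary endpoints are consistent across risk category, valve size, region and sex. The SAP leaves its exact method at the point where the samples are smallest, and gives no reason. A Greenwood-based interval carries no information when a subgroup has no deaths. It either collapses to a point, which makes ten patients look like certainty, or cannot be computed and leaves a gap in a safety table. In both cases the subgroup intervals cannot be set beside the exact interval for the whole cohort.

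The same sentence also applies Kaplan-Meier to paravalvular leak. That endpoint is a core-laboratory echo status at the 30-day visit and is analysed as a proportion in SAP 2.3.1.3 and 2.3.1.4.

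**Working it through.** The documents give no subgroup interval or zero-death probability to reproduce, so the check starts from their sizes and rates.

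**Subgroup sizes (Protocol section 3).**
- 23 mm valve: "with at least 10 subjects receiving a 23 mm valve", so a minimum of 10.
- 23 or 25 mm valve: a minimum of 40.
- Extreme risk: at most 20% of each analysis population "may be classified as extreme risk (n=33 subjects for the Portico NG cohort and n=12 for the Titan cohort").
- US subjects: a minimum of 85 in Portico NG and 30 in Titan.
- Sex in Portico NG: about 85 each. This is an assumption, based on the roughly 50% female share in the earlier IDE cohort (Protocol 5.4.3).

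The stated counts agree with their percentages: 0.20 × 169 = 33.8 (stated 33), 0.20 × 60 = 12, 0.50 × 169 = 84.5 (stated 85), 0.50 × 60 = 30.

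**Mortality (Protocol 1.1.1).** The range is 1.4% to 4.2% at 30 days, and the central value is the pooled 2.2%. No subgroup-specific rate is given, so these rates are applied to every subgroup as an assumption.

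**Step 1: the interval with no deaths.** Greenwood's variance is S² × Σ d/[n(n − d)], summed over event times. With every d = 0, S = 1 and the variance is 0 for any n. The plain interval for the death rate is then 0% to 0%. The log-log interval divides by log S = 0 and is undefined. Censoring does not help, because it changes n and not d.

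**Step 2: how often this happens.** P(0) = (1 − p)^n. For example, 0.978^10 = 0.80. The most likely count is the whole part of (n + 1)p.

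**Step 3: what the exact method would give.** With 0 deaths in n, the upper 95% Clopper-Pearson limit is 1 − 0.025^(1/n). For n = 10 this is 30.8%.

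| n | Subgroup | P(0) at 1.4% / 2.2% / 4.2% | Most likely count | Exact upper limit at 0 deaths |
|---|---|---|---|---|
| 10 | 23 mm, at minimum | 87% / 80% / 65% | 0 / 0 / 0 | 30.8% |
| 12 | Titan extreme risk, at cap | 84% / 77% / 60% | 0 / 0 / 0 | 26.5% |
| 30 | Titan US, at minimum | 66% / 51% / 28% | 0 / 0 / 1 | 11.6% |
| 33 | Portico NG extreme risk, at cap | 63% / 48% / 24% | 0 / 0 / 1 | 10.6% |
| 40 | 23 or 25 mm, at minimum | 57% / 41% / 18% | 0 / 0 / 1 | 8.8% |
| 85 | Portico NG US at minimum, or one sex | 30% / 15% / 3% | 1 / 1 / 3 | 4.2% |

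**Step 4: coverage on the plain scale.** A 0% to 0% interval excludes every positive true rate, so coverage cannot exceed 1 − P(0). At 2.2% that ceiling is 1 − 0.80 = 20% for n = 10 and 1 − 0.48 = 52% for n = 33, against a nominal 95%.

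**The case against.** The strongest reply is that little depends on this. The analyses are optional in the SAP and the protocol plans none. No subgroup interval enters the success criteria (Protocol 8.11, SAP 2.7), the sample size or the multiplicity statement. That stands, and it keeps the point to one about presentation. It does not rescue the method, which SAP 2.8 fixes if the analyses are done.

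Kaplan-Meier might also be defended as a way to handle early withdrawal. But SAP 2.3.1.1 and 2.3.1.2 do not use it for this endpoint. They take a binomial proportion and keep subjects who withdraw or are lost before the 30-day visit.

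Three stronger readings are tempting and are not supported.
- A reader might infer that no deaths is the most likely result in every subgroup named. SAP 2.8 gives no sizes. At about 85 subjects the most likely count is at least one, and at 30 to 40 subjects it is one when mortality is 4.2%.
- A reader might infer that the Greenwood interval is also wrong with one death, with a negative lower limit and an upper limit that is too low. That holds only without a transformation: 1 in 10 gives −8.6% to 28.6%, against an exact 0.3% to 44.5%. A log-log interval gives 1.5% to 52.7%, with an upper limit above the exact one. The SAP does not say which scale applies.
- A reader might infer that a 0% to 0% interval will certainly be printed. On the log-log scale the interval would be missing instead.

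**Conclusion.** The point holds in a limited form. If the subgroup analyses are run as SAP 2.8 states, any subgroup with no deaths gets no usable mortality interval, whichever of the two scales is used. No deaths is the most likely result across the whole cited mortality range at n = 10 and n = 12. It is common at n = 30 to 33 (24% to 66%) and is not the most likely result at about 85 (3% to 30%). Where it occurs, the data would still be compatible with 30-day mortality of up to 30.8%, 26.5%, 11.6% or 10.6% for n = 10, 12, 30 or 33.

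These probabilities assume the cited overall mortality in each subgroup, and subgroup sizes at the stated minimums or caps. A higher rate in extreme-risk subjects would lower their chance of no deaths, and a 23 mm group above its minimum would lower it too. Fewer extreme-risk subjects than the cap would raise it. The primary test and the study conclusions are unaffected.

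**What to change.** Replace the Kaplan-Meier sentence in SAP 2.8 with: *Subgroup rates for both primary endpoints (30-day all-cause mortality and moderate or greater PVL at 30 days) will be reported as binomial proportions with exact Clopper-Pearson 95% confidence intervals, using the same analysis populations as in Section 2.3.1.*

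The wording covers paravalvular leak because the current sentence does. Pointing to Section 2.3.1 carries over its rules on early withdrawals, COVID-19 related deaths and the implanted population.

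SAP 2.8 and Protocol 8.5 should also be reconciled, so that both say whether subgroup analyses are planned, optional or absent.

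The cost is one SAP sentence and one reconciling edit. No new data are needed, the programming is simpler, and the primary test and success criteria do not change. The zero-death subgroups will show wide intervals, which is what their size supports.

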### 2.9 Handling of Missing Data

All analyses will be performed on available data and additional considerations due to the COVID-19 pandemic are detailed in Section 2.2.4 and in the primary and secondary endpoint sections.

### 2.10 Poolability

To assess poolability of the primary safety and effectiveness endpoints across sites, Fisher's exact test will be used to test the rate of a subject with a primary endpoint event within each site. If the primary endpoint by site is significant at the 0.15 significance level, the clinical relevance will be considered, additional analyses will be performed to determine if differences in the distributions of baseline factors account for site differences, and primary endpoints be presented at the site level. In the pooling analysis, investigational sites that have less than five (5) subjects enrolled will be grouped as one 'small' center for the purpose of this analysis. If the number of subjects in this "small" center exceeds the total number of subjects enrolled in the "biggest" site, then multiple small sites will be created based on geographic region as appropriate. Poolability analysis will be performed for both the Portico NG and Titan cohorts independently.

### 2.11 Multiplicity

The clinical study has two (2) co-primary endpoints with hypothesis testing only for the primary effectiveness endpoint in the Portico NG cohort. Therefore, there is no multiplicity adjustment planned in this clinical study.

### 2.12 Adjustments for Covariates

Unless otherwise specified, no adjustments for covariates will be made for any of the variables in the analyses.

### 2.13 Sensitivity Analysis

For the primary safety endpoint, a sensitivity analysis will be conducted including all CEC adjudicated death events regardless relationship to COVID-19 to assess the impact of the pandemic. Sensitivity analysis will also be conducted including all CEC adjudicated VARC-2 events regardless to COVID-19 to assess the impact of the pandemic. Sensitivity analysis on the primary endpoint and the VARC-2 event rate will be performed for both the Portico NG and Titan cohorts independently.

## Statistical Analysis Plan

### 3.0 DESCRIPTIVE ENDPOINTS AND ADDITIONAL DATA

#### 3.1 Baseline and Demographic Characteristics

The following baseline and demographic variables will be summarized separately for the subjects enrolled in both the Portico NG and Titan cohorts: gender, age, ethnicity, race, surgical risk, medical comorbidities, arrhythmia history, previous pacemaker implant, history of smoking, implant procedural characteristics, etc.

#### 3.2 Adverse Events

All adverse events, serious adverse events (SAEs), unanticipated serious adverse device effects (USADEs) will be summarized for all subjects in the attempted population in this trial in terms the number of events and the number of subjects, as well as the percentage of subjects with events per AE term if relevant for the specific analysis. All CEC adjudicated adverse events will also be summarized for all subjects who underwent an implant attempt in terms the number of events, the percentage of subjects with events. Moreover, COVID-19 related AEs will be summarized in terms of number of events and the number of subjects, as well as the percentage of subjects with events per AE term if relevant for the specific analysis. AE summaries will be presented for both the Portico NG and Titan cohorts independently.

